4.2 Intervention

Patients will be treated with intralesional injections of talimogene laherparepvec on Week 1 and every three weeks thereafter and intravenous pembrolizumab on Week 1 and every three weeks thereafter, for up to 35 cycles. Patients who discontinue study therapy after a maximum of 35 cycles of study therapy will be allowed to resume study therapy in the setting of progression of disease off study therapy. In the additional neoadjuvant cohort, patients will receive up to 8 cycles of study therapy beginning on Week 1. On completion of surgery, pembrolizumab alone will continue as tolerated for a total of 17 cycles (neoadjuvant and adjuvant therapy).

Talimogene laherparepvec will be administered intralesionally into injectable cutaneous, subcutaneous, accessible superficial or deep soft tissue and nodal lesions with or without ultrasound guidance. Talimogene laherparepvec must not be administered into visceral organ metastases. The initial dose of talimogene laherparepvec is up to 4.0 mL of 10^6 plaque-forming units (PFU)/mL on Week 1. Subsequent doses of talimogene laherparepvec are up to 4.0 mL of 10^8 PFU/mL on Week 4 and subsequent doses thereafter. When talimogene laherparepvec and pembrolizumab are administered on the same day, talimogene laherparepvec will be administered first.

Pembrolizumab at a dose of 200mg/dose will be administered intravenously at Week 1 and every 3 weeks (± 3 days) thereafter. Pembrolizumab infusion should be administered in 30 minutes, with a window of -5 and +10 minutes, using an infusion pump.

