11.1 Adverse Event Characteristics and Definitions

11.1.1 Definitions of Treatment Related Toxicity Events (TRTE) and decisions based on TRTEs:

Subjects are considered evaluable for feasibility and toxicity assessments if they receive at least one dose of the protocol-assigned dose(s). The treatment related toxicity events that determine feasibility and early-stopping results are defined as those that result in:

- i) study drug(s) discontinuation or
- ii) delay in study drug administration more than 9 weeks from the date of the planned dose (i.e., approximately 12 weeks since the previous dose)

TRTE will be evaluable throughout the study period. The events will only be considered TRTE if judged by the investigator to be related to the administration of talimogene laherparepvec and/or pembrolizumab.

Examples include

- Grade 4 non-hematologic toxicity
- Grade 3 or greater immune-mediated adverse events (except skin).
- Any grade plasmacytoma at or near the injection site or evidence of impaired wound healing at the injection site
- Grade 3 or greater allergic reactions considered at least possibly related to talimogene laherparepvec or pembrolizumab.
- Grade 3 or higher pneumonitis
- Grade 3 non-hematologic toxicity lasting > 3 days despite optimal supportive care
- Any grade 3 or higher non-hematologic laboratory value if:
 - o medical intervention is required, or
 - o the abnormality leads to hospitalization, or
 - o the abnormality persists for > 1 week
- Febrile neutropenia grade 3 or grade 4.
- Thrombocytopenia $< 25 \times 10^9/L$
- Grade 5 toxicity (i.e., death)

The following herpetic events:

- Serious herpetic events such as herpetic encephalitis, encephalomyelitis or disseminated herpetic infection
- For any herpetic events confirmed due to talimogene laherparepvec that require treatment with acyclovir or similar anti-viral agent, treatment with talimogene laherparepvec should be suspended if anti-viral treatment is required with systemic acyclovir or other anti-virals, and if ongoing anti-viral treatment is required, treatment with talimogene laherparepvec should be permanently discontinued

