Herpetic events due to wild-type HSV-1 or wild-type HSV-2 which require acyclovir and are not due to talimogene laherparepvec (as confirmed by PCR testing) should not be considered as treatment related toxicity event caused by talimogene laherparepvec. Subjects may be replaced if they are not evaluable for feasibility and treatment related events (e.g., a subject did not receive both study drugs or permanently discontinued talimogene laherparepvec prior to receiving the first dose of pembrolizumab for any reason).

If dosing is delayed by more than 9 weeks from the date of the planned dose (i.e., approximately 12 weeks since the previous dose) due to the occurrence of an adverse event that is considered related to talimogene laherparepvec and/or pembrolizumab, then the subject should be taken off study treatment(s) that the adverse event is deemed to have been related to (see section 11.4.1).

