12.2 Definitions

Evaluable for toxicity – All patients will be evaluable for toxicity from the time of their first treatment with talimogene laherparepvec and/or pembrolizumab.

Evaluable for efficacy – Only those patients who have a measurable disease based on RECIST 1.1 criteria will be eligible for this study, as highlighted in Section 6.0. These patients will have their response classified according to the definitions stated below.

Only those patients who have measurable disease present at baseline, have received at least one cycle of therapy, and have had their disease re-evaluated will be considered evaluable for response. (Note: Patients who exhibit objective disease progression prior to the end of cycle 1 will also be considered evaluable. Note: one cycle of therapy consists of 21 days where the study therapy (TVEC and pembrolizumab) is administered at the start of the cycle on day 1)

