Patients evaluable for efficacy analysis will include all patients treated with talimogene laherparepvec or pembrolizumab and assessable for response. Patients who are missing an assessment of response post baseline will not be considered evaluable for response unless they missed the assessment due to progression of disease in which case they will be considered non-responders for that time point. Patients who miss an assessment of response post baseline for any reason other than progression of disease will be replaced.

Patients evaluable for safety analysis will include all patients who have received at least one dose of talimogene laherparepvec and pembrolizumab.

We expect to accrue approximately 1-2 patients each month and hence expect to finish enrollment in 10-20 months.

Additional cohorts:

Locally advanced/metastatic cohorts:

Primary End Point

The primary objective is to evaluate the efficacy of the combination therapy in each subtype-specific cohort, as assessed by the best objective response rate (complete response + partial response). The primary endpoint is best objective response rate (RECIST 1.1). It will be estimated for each subtype-specific cohort, as the proportion of evaluable patients who have complete response and partial response as defined by RECIST 1.1 criteria, with a two

sided 95% CI provided. The lower limit of the CI allowed by a sample size of 10 is provided for a range of possible ORR in the below table.

Table 15. 95% CI for estimating ORR for a Sample Size of 10 Patients

Estimated ORR	0.20	0.30	0.40	0.50
CI 95%	0.03~0.56	0.07~0.65	0.12~0.74	0.19~0.81

Patients evaluable for efficacy analysis will include all patients who have received at least one cycle of treatment with T-VEC and pembrolizumab and are assessable for response. Patients who are missing an assessment of response post baseline will not be considered evaluable for response unless they missed the assessment due to progression of disease or treatment related toxicities in which case they will be considered non-responders for that time point. Patients who miss an assessment of response post baseline for any reason other than progression of disease and treatment related toxicity will be replaced.

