In relation to the design of the additional locally advanced/metastatic cohorts, there will be 3 histology specific groups: i) cutaneous angiosarcoma, ii) epithelioid sarcoma, and iii) undifferentiated pleomorphic sarcoma/myxofibrosarcoma. These sarcoma subtypes reflect the subtypes where clinical activity was demonstrated in the phase II study to date.

We expect to accrue approximately 1-2 patients each month and hence expect to finish enrollment in 15-30 months.

Secondary endpoints

1. Safety

Patients evaluable for safety analysis will include all patients who have received at least one dose of T-VEC and pembrolizumab. Adverse events will be graded according to the NCI CTCAE v4.03, presented on an individual basis and summarized using descriptive statistics.

2. Survival

Progression free survival (PFS) rate at 24 weeks, median PFS, overall survival (OS) and progression-free survival intervals will be estimated using Kaplan-Meier methodology

3. Best Objective Response Rate by irRECIST

Best objective response rate (complete response + partial response) by 24 weeks by immune-related response criteria (irRECIST), of T-VEC in combination with pembrolizumab in patients with metastatic and/or locally advanced, sarcoma.

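### Section 14.1 limits the safety set to patients dosed with both drugs, which conflicts with section 12.2 and the opening definition of section 11.1.1 and can drop a patient because of T-VEC toxicity

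*Combined protocol and SAP*

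**What the plan says.** **Safety set.** For the first 20 patients, section 14.1 (Primary and Secondary Endpoints Statistical Considerations) takes "all patients who have received at least one dose of talimogene laherparepvec and pembrolizumab". For the additional cohorts the same section takes "all patients who have received at least one dose of T-VEC and pembrolizumab".

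**Efficacy set, first 20 patients.** A paragraph earlier, section 14.1 uses the other connective: "all patients treated with talimogene laherparepvec or pembrolizumab and assessable for response".

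**Toxicity evaluability.** Section 12.2 (Definitions) says: "All patients will be evaluable for toxicity from the time of their first treatment with talimogene laherparepvec and/or pembrolizumab". Section 11.1.1 opens by calling a subject evaluable for feasibility and toxicity after at least one assigned dose. It counts an event if it is "judged by the investigator to be related to the administration of talimogene laherparepvec and/or pembrolizumab".

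**Replacement.** Later in section 11.1.1, subjects who are not evaluable for feasibility and treatment-related events may be replaced. The example given is that "a subject did not receive both study drugs or permanently discontinued talimogene laherparepvec prior to receiving the first dose of pembrolizumab for any reason".

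**Order of dosing.** Section 4.2: "When talimogene laherparepvec and pembrolizumab are administered on the same day, talimogene laherparepvec will be administered first". Both drugs start in Week 1.

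**Stopping rule.** Section 14.1 stops the trial at 2/4, 3/8, 4/14 or 5/20 patients with a qualifying event, as defined in section 11.1.1. It states a stopping probability of about 10% at a true event rate of 10%, and about 79% at 30%.

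**The concern.** A safety population should be fixed by exposure, not by what happened after exposure. Under section 14.1 as written, entry requires the second drug. A patient given T-VEC who reacts badly enough that pembrolizumab is never started has been exposed and harmed, yet is outside the set. The reason for exclusion is then the outcome the set is meant to describe, so the summary can only err towards looking safer.

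A second question concerns feasibility, which is a secondary endpoint judged by whether the toxicity boundary is crossed. The replacement sentence in section 11.1.1 covers discontinuation for any reason and makes no exception for toxicity. Read strictly, it would let a patient with a qualifying event be declared not evaluable and replaced.

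**Working it through.** **Step 1: place one patient in each definition.** The patient receives T-VEC at Week 1, has a treatment-related toxicity, and never receives pembrolizumab.

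| Place | Rule | Patient included? |
|---|---|---|
| 14.1, safety, first 20 | both drugs | No |
| 14.1, safety, additional cohorts | both drugs | No |
| 14.1, efficacy, first 20 | either drug, if assessable | Can be |
| 12.2, toxicity | either drug | Yes |
| 11.1.1, opening sentence | at least one dose | Yes |
| 11.1.1, replacement sentence | both drugs, otherwise replaceable | No |

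The conflict between 14.1 and 12.2 is clean. Section 11.1.1 is divided: its opening sentence agrees with 12.2 and its replacement sentence agrees with 14.1. The "or" in the first-20 efficacy set argues against treating the "and" in the safety set as loose drafting. That contrast is not available for the additional cohorts, where the efficacy set also asks for both drugs.

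**Step 2: reproduce the stated stopping probabilities.** Inputs are the boundaries and the 10% and 30% rates from section 14.1. I used an exact binomial recursion, patient by patient, stopping at 2 or more events within the first 4 patients, 3 within 8, 4 within 14 and 5 within 20.

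- Crossings through patient 19 (a crossing at the last patient is not an early stop): 9.9% at a 10% rate and 78.8% at 30%. These match the stated 10% and 79%.
- Crossings through patient 20: 10.4% and 81.6%. The second does not match 79%, so I use the first convention below.

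**Step 3: illustrate exclusion with replacement.** Assumption: a fraction f of event patients have the event after T-VEC, never receive pembrolizumab, and are excluded and replaced. The documents give no value for f. The event rate p among those still counted becomes

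p′ = p(1 − f) / (1 − pf).

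For p = 0.30:

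- f = 5%: p′ = 0.285/0.985 = 0.289; chance of stopping 76.0%
- f = 10%: p′ = 0.270/0.970 = 0.278; chance of stopping 72.8%
- f = 20%: p′ = 0.240/0.940 = 0.255; chance of stopping 65.4%

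For p = 0.10 the chance of stopping goes from 9.9% to 8.9%, 7.9% and 6.1% for the same values of f.

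**Step 4: a single patient.** If the first patient has such an event and the true rate is 30%, the chance of stopping is 91.9% when it is counted. It is 78.8% when the patient is replaced and the count starts afresh.

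**The case against.** The strongest reply is that the stopping rule does not use the section 14.1 safety set. The rule counts events as defined in section 11.1.1, which opens with a one-dose criterion and accepts events related to either drug. Only the replacement sentence could change the count. That sentence is permissive and does not say that a replaced patient's event is deleted. Section 13 includes patients in the safety and/or efficacy analyses unless otherwise stated. This stands. A reader might infer that the safety-set wording biases the stopping rule downward, but the documents support only that the count is unclear.

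The window is also short. Both drugs start on the same day, and several listed events (toxicity lasting more than 3 days, plasmacytoma, a delay beyond 9 weeks) cannot arise within hours. An acute reaction is the realistic route. Section 11.4.1 allows pembrolizumab to continue after toxicity that is clearly T-VEC's alone, and such a patient would then enter the set. In the phase Ib melanoma study described in section 3.5, pembrolizumab began on day 36 and none of 21 patients discontinued for adverse events. That evidence is indirect, but it supports expecting few cases.

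The event would not vanish from the record. Adverse events are collected from the first dose (11.6.1), all go into line listings (17.2.1), the DSMC reviews the trial (16.2), and the safety analysis is descriptive. This limits the harm but does not repair a summary whose denominator omits an exposed patient.

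Finally, the rule is stated only for the first 20 patients, whose response results already appear in section 4.1, and section 16.3 describes the study as completed. No stopping rule is stated for the additional cohorts. So the remaining effect is on reporting, not on a live stopping decision.

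**Conclusion.** The point holds as a wording conflict with a real but small consequence. Sections 14.1 and 12.2 give different safety populations, and the patient on whom they differ can be one excluded because of toxicity. Section 11.1.1 contradicts itself on the same patient, so it would be too strong to say that 14.1 conflicts with all of 11.1.1.

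The number affected is probably very small and may be zero. The fall from about 79% to between 76% and 65% rests on an assumed f of 5% to 20%, and on reading the replacement sentence as removing the event. It is an illustration, not an estimate.

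A reader might also be tempted to say that the reported toxicity rate would be halved, from 2/20 = 10% to 1/19 = 5.3% (or 1/20 = 5% if the replacement has no event). That supposes two events, one of them in a patient who never reached pembrolizumab. Nothing in the documents supports such a share.

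What matters now is the safety and feasibility reporting for the first 20 patients and the safety summaries of the additional cohorts, where one patient in 10 is 10 percentage points.

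**What to change.** 1. In both places in section 14.1, define the safety set as every patient who received any dose of T-VEC and/or pembrolizumab, in line with section 12.2.
2. Reconcile the replacement sentence in section 11.1.1 with that section's opening definition. A patient may still be replaced for other purposes, but treatment-related toxicity in a replaced patient should count in the safety summary and in the toxicity (feasibility) count.
3. In the report, state how many patients received only one drug and why. If there were none, say so; the two definitions then give the same results.

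The cost is a wording amendment and its routine review, which under section 16.3.1 means the T-VEC manufacturer and then the institutional review board. No sample size, dose or visit changes. Because the first 20 patients have already been enrolled, the amendment should say that it clarifies who is counted and is not a new monitoring rule.

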Following enrolment of the first 20 patients on this study additional cohorts will open. In the initial 20 patients enrolled on this study, the ORR overall was 35% and the ORR at 24 weeks was 30%. Objective response was observed in 5 histological subtypes including UPS, myxofibrosarcoma, cutaneous angiosarcoma, epithelioid sarcoma and undifferentiated sarcoma not otherwise specified. The additional cohorts will include a total of 40 patients and will be divided into 4 cohorts. Thirty patients with inoperable, locally advanced/metastatic sarcoma will be enrolled onto one of 3 cohorts based on sarcoma-specific subtype [i) UPS/myxofibrosarcoma, ii) epithelioid sarcoma, iii) cutaneous angiosarcoma]. Each cohort will enroll 10 patients. Patients with inoperable, locally advanced/metastatic sarcoma will be treated following the study design as highlighted above.

In the metastatic/locally advanced cohort, patients who achieve a CR or complete disappearance of the injectable lesion may stop intralesional injections of talimogene laherparepvec, but treatment with pembrolizumab will be continued. Study therapy may continue for a total of 35 cycles in the absence of confirmed progression of disease or clinical progression, disappearance of injectable lesions (talimogene laherparepvec only), intercurrent illness that prevents further administration of treatment, or intolerance of study treatment. Patients who discontinue study therapy after a maximum of 35 cycles of study therapy will be allowed to resume study therapy for an additional 17 cycles in the setting of progression of disease off study therapy. In the neoadjuvant setting, TVEC and pembrolizumab will continue for up to 8 cycles prior to surgical resection. On completion of surgery pembrolizumab alone will continue as tolerated for a total of 17 cycles (neoadjuvant and adjuvant therapy). Safety data will be collected for up to 30 days following surgical resection.

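### For the expansion cohorts, Sections 14.1, 12.2 and 13.0 disagree on whether a patient who stops early for treatment-related toxicity without a response scan is in the primary ORR denominator

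*Combined protocol and SAP*

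**What the plan says.** Section 4.1 sets the size: "Each cohort will enroll 10 patients". Section 14.1 (additional cohorts) makes ORR in each histology cohort the primary endpoint. It is estimated as "the proportion of evaluable patients who have complete response and partial response as defined by RECIST 1.1 criteria" with a two-sided 95% interval, and Table 15 shows the intervals for n = 10.

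The same part of Section 14.1 then gives three rules:

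1. Entry: the efficacy set is "all patients who have received at least one cycle of treatment with T-VEC and pembrolizumab and are assessable for response".
2. Missing assessment: a patient with no post-baseline assessment is not evaluable unless it was missed "due to progression of disease or treatment related toxicities in which case they will be considered non-responders for that time point".
3. Replacement: patients who miss an assessment "for any reason other than progression of disease and treatment related toxicity will be replaced".

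Two other sections bear on the same patients, and neither is limited to the initial 20.

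- Section 12.2 states that "one cycle of therapy consists of 21 days", with both drugs given on day 1. To be evaluable for response a patient needs at least one cycle and a disease re-evaluation. The only exception is objective progression before cycle 1 ends; toxicity is not mentioned.
- Section 13.0 permits replacement of a patient who leaves the study before the second dose for a reason other than progression. It requires replacement of a patient who misses a post-baseline assessment for a reason other than progression. Toxicity is not exempted from either rule.

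The first response scan is at week 8 (Section 10.2).

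**The concern.** The non-responder rule in Section 14.1 is the sound one: a patient who could not stay on treatment because of its toxicity did not respond, and should count. The other provisions can take that patient out again, either through the one-cycle and re-evaluation conditions or through replacement by someone else. Every patient removed this way is a treatment failure, so the error runs in one direction and raises ORR. With 10 patients per cohort, one such patient is visible in the result. An analyst following Section 12.2 or 13.0 and one following the non-responder rule in Section 14.1 could report different primary results from the same data.

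**Working it through.** **Step 1. Apply each rule to one patient.** Take a patient who receives both drugs on day 1, stops for treatment-related toxicity during cycle 1 (say on day 10), and has no response scan.

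| Provision | Outcome |
|---|---|
| 14.1, missing-assessment and replacement rules | Non-responder, not replaced |
| 14.1, entry condition, if a cycle means completing 21 days | Outside the set |
| 14.1, entry condition, if the day-1 doses make a cycle | Entry condition met |
| 12.2, re-evaluation condition | Not evaluable |
| 13.0, leaving before the second dose | May be replaced |
| 13.0, missed assessment not due to progression | Must be replaced |

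The last three rows disagree with the first whichever meaning of a cycle is chosen.

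**Step 2. Reproduce Table 15.** The exact (Clopper-Pearson) limits for x responders of n are the 2.5% quantile of Beta(x, n−x+1) and the 97.5% quantile of Beta(x+1, n−x). For n = 10:

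- x = 2: 0.025–0.556
- x = 3: 0.067–0.652
- x = 4: 0.122–0.738
- x = 5: 0.187–0.813

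These match the table, so the method is exact and the denominator is 10.

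**Step 3. Effect on the estimate.** Let k be the number of such patients in a cohort (an assumption) and suppose 3 responders.

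| k | Counted, 10 treated | Excluded, not replaced | Replaced: reported | Replaced: all treated |
|---|---|---|---|---|
| 0 | 3/10 = 30.0% (6.7–65.2) | same | same | same |
| 1 | 3/10 = 30.0% | 3/9 = 33.3% (7.5–70.1) | 3/10 = 30.0% | 3/11 = 27.3% (6.0–61.0) |
| 2 | 3/10 = 30.0% | 3/8 = 37.5% (8.5–75.5) | 3/10 = 30.0% | 3/12 = 25.0% (5.5–57.2) |

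Over the range of Table 15, one patient excluded without replacement moves ORR by 2 to 6 points (2/10 = 20.0% to 2/9 = 22.2%; 5/10 = 50.0% to 5/9 = 55.6%).

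**Step 4. Dependence on the rate.** Let t be the proportion of treated patients who stop this way, none of whom responds, and p the response probability among all treated. Among the rest it is p/(1−t), with or without replacement. The factor 1/(1−t) is 1.00 at t = 0, 1.05 at 5%, 1.11 at 10% and 1.43 at 30%. For p = 30% this gives 30.0%, 31.6%, 33.3% and 42.9%. The documents give no value for t. The 10% and 30% points are the acceptable and unacceptable rates of the initial-20 stopping rule in Section 14.1, used here only as upper-end values.

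**The case against.** The strongest reply is that Section 14.1 can be read as one coherent rule. It asks for at least one cycle and does not say that the cycle must be completed. All dosing in a cycle falls on day 1, so a patient given both drugs who stops on day 10 can be said to have received one. The missing-assessment rule then keeps that patient as a non-responder. A reader might infer that Section 14.1 flatly contradicts itself by demanding a full cycle; the text does not go that far. This part of the reply stands: Section 14.1 alone is ambiguous. The benign reading is not secure, however. If day-1 dosing were enough, the exception in Section 12.2 for progression before the end of cycle 1 would be largely redundant. The safety set in Section 14.1 is also defined by a dose, which suggests that a cycle means something else.

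It could also be argued that the cohort-specific text in Section 14.1 overrides the general text elsewhere. No order of precedence is stated, and Sections 12.2 and 13.0 are not confined to the initial 20.

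A reader might further infer that cohorts will shrink below 10 and that Table 15 will cease to apply. That is only one reading, because Section 13.0 would replace these patients.

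A reader might also put the 10% acceptable toxicity rate into 1 − 0.9^10 = 65% and take it as the chance that a cohort is affected. The documents do not support that use. The rate was set for the initial 20, covers the whole study period, and includes dosing delays of nine weeks or more, which cannot occur inside a 21-day cycle. Section 14.1 also cites 0% discontinuation for treatment-related events in the earlier melanoma combination study. Pembrolizumab started on day 36 there (Section 3.5), so that figure says little about a concurrent start.

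Finally, these cohorts are for estimation and carry no decision threshold, and a shift of about 3 points is small beside an interval about 58 points wide (65.2 − 6.7 = 58.5). That stands as a limit on the size. It does not remove a bias that always runs upward.

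**Conclusion.** The concern holds as a conflict between sections. Section 14.1 keeps patients who miss assessment through treatment-related toxicity as non-responders. Section 12.2 can make them non-evaluable, and Section 13.0 replaces them. The entry condition in Section 14.1 adds an ambiguity and is not a proven self-contradiction.

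The effect is upward and modest: about 3 points for one such patient in a cohort with 3 responders, under either exclusion or replacement, and 5 to 7.5 points for two. This assumes that the patient has no scan and would count as a non-responder. If no patient stops this way there is no effect. The documents do not allow the likelihood to be estimated, so neither the 65% figure nor a claim that cohorts will fall below 10 should be attached to the point.

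**What to change.** In Section 14.1 (additional cohorts), define the efficacy set as all patients who received at least one dose of study treatment, and state whether one of the two drugs suffices. State that patients who miss assessment because of progression or treatment-related toxicity count as non-responders and are not replaced.

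For these cohorts, add the same toxicity exception in two places: the one-cycle and re-evaluation conditions in Section 12.2, and both replacement rules in Section 13.0. Changing Section 14.1 alone would leave the conflict in place. The changes should be limited to the expansion cohorts, because Section 4.1 already reports the response rate of the initial 20.

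If the data have already been collected, the definition can still be fixed for reporting, labelled as a later clarification, with ORR among all treated patients shown beside it.

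The cost is wording in three sections and an ORR that may be a few points lower. Sample size and visits do not change.
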